8.9 Analysis Software

All analyses will be performed using SAS® Software version 9.2 or higher.

9. STUDY SUBJECTS

9.1 Disposition of Subjects and Withdrawals

All enrolled subjects will be accounted for in this study. The numbers and percentages of subjects in each analysis set, study withdrawals, subgroups, and major protocol deviations will also be presented.

The time the subjects are under observation will be summarized by vaccine group and overall and by study period using summary statistics (mean, standard deviation (SD), minimum, median, maximum)

10. DEMOGRAPHICS AND OTHER BASELINE CHARACTERISTICS

In general, all tables presented in CSR section 14.1 should show a Total column across vaccine groups.

10.1 Demographics

Age, height, weight, body mass index will be summarized by reporting the mean, standard deviation, median and range, and will be calculated by vaccine group, country and overall.

In addition, the frequencies of age categories will be reported as 65-74 years old vs. ≥ 75 years old (age as a randomization stratum) and 65-74 vs 75-84 vs. ≥ 85 years old. The number and percentages of subjects by sex, country, age categories (for posting), ethnic origin, race, entry criteria fulfilled, by previous vaccination (in past 5 years), smoking status and comorbidity will be presented by vaccine group and overall. Demographic data will be tabulated for the All Enrolled, FAS (demography), PPS and Safety sets.

10.2 Medical History

The numbers and percentages of subjects with medical history will be presented by Medical Dictionary for Regulatory Activities (MedDRA) system organ class (SOC) and preferred term (PT) by vaccine group and overall. Medical history data will be tabulated for the All Enrolled, FAS (demography), PPS and Safety Sets.

11. IMMUNOGENICITY ANALYSIS

Where applicable, immunogenicity objectives will be evaluated using Center for Biologics Evaluation and Research (CBER) Guidance Clinical Data Needed to Support the Licensure of Seasonal Inactivated Influenza Vaccines (CBER 2007).

For the elderly population the CBER criteria are as follows:

- the lower bound of the two-sided 95% confidence interval (CI) for the percent of subjects achieving seroconversion for HI antibody should meet or exceed 30%
- the lower bound of the two-sided 95% CI for the percent of subjects achieving an HI antibody titer $\geq 1:40$ should meet or exceed 60%.

Both endpoints should be met for each strain included in the vaccine.

11.1 Blood Samples

The numbers and percentages of subjects with blood draws will be summarized overall and by vaccine group where applicable. Data will be tabulated for the immunogenicity subset.

11.2 Primary Objectives Analysis

Not Applicable

11.3 Secondary Objectives Analysis

The following secondary immunogenicity analyses will be performed:

1. Geometric mean HI titer (GMT) on Days 1 and 22.
2. Geometric Mean Ratios (GMRs) AT Day 22/ Day 1.
3. Percentage of subjects achieving seroconversion (defined as: HI $\geq 1:40$ for subjects negative at baseline [$<1:10$]; or a minimum 4-fold increase in HI titer for subjects positive at baseline [HI $\geq 1:10$]) on Day 22.
4. Percentage of subjects with HI titer $\geq 1:40$ on Day 22.
5. Reverse cumulative distribution plots will be generated in order to display the distribution of the antibody responses at Day22.

CBER requirements for each vaccine group translate into the following hypothesis:

$$H_{0k}^{(SC)}: \pi_{ik} - \pi_0 \leq 0 \quad \text{vs.} \quad H_{1k}^{(SC)}: \pi_{ik} - \pi_0 > 0$$
$$H_{0k}^{(SP)}: \tau_{ik} - \tau_0 \leq 0 \quad \text{vs.} \quad H_{1k}^{(SP)}: \tau_{ik} - \tau_0 > 0,$$

assuming that responses Y_{ij} , Z_{ij} are independent identically distributed Bernoulli variables $B(1, \pi_{ik})$ and $B(1, \tau_{ik})$, where i denotes vaccine group; $j=1, \dots, n_i$ denotes subject, k denotes strain, π_{ik} and τ_{ik} represent the population proportions of subjects achieving seroconversion and post-vaccination HI titer $\geq 1:40$, respectively, π_0 and τ_0 denote the thresholds for seroconversion ($\pi_0 = 0.3$) and the threshold for proportion of subjects with HI titer $\geq 1:40$ ($\tau_0 = 0.6$).

All hypothesis related to CBER criteria will be tested on unadjusted two-sided 5% significance level.

Secondary immunogenicity objectives will be evaluated based on the FAS (immunogenicity). If the percentage of vaccinated subject excluded from the FAS (immunogenicity) is greater than 5%, a secondary analysis based on the PPS will be performed to complement the FAS.

All statistical analyses for HI titers will be performed on the logarithmically (base 10) transformed values. Individual HI titers below detection limit (for example <10) will be set to half of that limit (5).

Estimates for GMTs, GMRs and pertaining 2-sided 95% CIs will be calculated assuming log-normal distribution of the titers and will be completed by providing minimum, maximum and median titers for each vaccine group.

Binary data (i.e., percentages of subjects with seroconversion and with titer $\geq 1:40$) will be summarized using unadjusted estimates and will be reported together with 2-sided 95% Clopper and Pearson CIs ([Clopper and Pearson 1934](#)). Differences of proportions will be reported with 95% CI calculated using Miettinen and Nurminen's method ([Miettinen and Nurminen 1985](#))'s method.

No multiplicity adjustment to the CI levels will be implemented.

Reverse Cumulative Distribution Curve will be generated in order to display the distribution of the antibody responses at Day 22.

11.4 Exploratory Objectives Analysis

The following exploratory immunogenicity analyses will be performed:

1. Geometric mean MN titer (GMT) on Days 1 and 22.

2. Ratio of Geometric mean MN titer (GMTr) of aQIV versus Non-influenza comparator at Day 22.
3. Percentage of subjects with a four-fold rise in MN antibody titer at Day 22.
4. Reverse cumulative distribution plots will be generated in order to display the distribution of the MN antibody responses at Day22.

Exploratory objectives related to the MN-assay will be evaluated using methods for lognormal and binomial data as described in the [Section 11.3](#).

Additionally, an estimate of the serologic correlate of protection on the basis of HI or other immunological responses including MN, measured three weeks after vaccination against the respective strain.

Evaluation of a Serological Predictor of Protection Against Influenza

The immunogenicity data of the blood draw 21 days after vaccination from all subjects reporting an influenza case and subjects randomized from the population without an influenza case serving as the control group will be used to evaluate the relationship between antibody levels tested with the HI assay and clinical protection from influenza.

The Prentice criterion will be used to assess, whether an immunologic correlate of protection can be determined.

To accommodate the criterion a linear logistic regression model will be fitted with vaccine group included as independent predictor and incidence of influenza as dependent variable to show that the observed vaccine effect be explained in a statistical model using immunologic data.

A second logistic regression model will be fitted, adjusted for log-transformed antibody titer and vaccine group to determine the effect of antibody titer on the incidence of influenza. Then, the relationship between the occurrence of influenza and antibody titer level will be modeled using the logistic regression model advocated by Dunning that accommodates both antibody titers and factors independent of antibody titers.

In this model, the probability that a subject develops influenza is the probability that the subject is susceptible multiplied by the probability that susceptible individuals develop disease. Susceptibility is characterized by the probability 1, and the probability that a subject with titer t is protected is represented by a 2-parameter logit function. Analyses

will be conducted to determine the level of HI (or other assays that might be performed) antibody titer associated with 50%, 60%, 70%, 80% and 90% probability of protection.

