End of influenza season: The end of the influenza season will be defined as the end of June for Northern Hemisphere (NH) influenza season and end of December for Southern Hemisphere (SH) influenza season. For tropical countries, with no typical NH or SH influenza season, the season is defined by the use of the strains in the vaccine formulation (i.e. strains as recommended for the NH or the SH influenza season) and the timing of vaccination.

Influenza case: An ILI associated with RT-PCR or culture confirmed influenza.

ILI onset: The first day on which a subject fulfils the criteria for protocol-defined ILI.

Medically-attended Adverse Event³: Defined as symptoms or illnesses requiring hospitalization, or emergency room visit, or visit to/by a health care provider.

Modified CDC Influenza-like illness (ILI)⁴: Fever (temperature of $> 37.2^{\circ}\text{C}/99^{\circ}\text{F}$) with cough or sore throat.

Protocol-defined ILI: At least one of the following respiratory symptoms: sore throat, cough, sputum production, wheezing, or difficulty breathing; concurrently with at least one of the following systemic symptoms: temperature of $> 37.2^{\circ}\text{C}/99^{\circ}\text{F}$, chills, tiredness, headache, or myalgia.

Qualified healthcare professional: Any licensed health care professional who is permitted by institutional policy to perform clinical interventions and assessments such as physical examinations and who is identified within the Study Staff Signature Log.

Trained healthcare professional: Any health care professional who is permitted by institutional policy and trained to perform delegated tasks and who is identified within the Study Staff Signature Log.

³ Please also refer to the CRF instructions for further guidance.

⁴ The respiratory symptoms in both definitions are considered a new onset or exacerbation of a pre-existing condition.

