2. OBJECTIVES

2.1 Primary Objective(s)

The primary and secondary efficacy objectives will be measured in all subjects in relation to cases of influenza occurring from 21 through 180 days after vaccination or through the end of influenza season, whichever is longer. In all cases, efficacy will be determined based on influenza cases caused by A (H1N1 and H3N2) and either B lineage.

Primary Efficacy Objective:

1. To demonstrate absolute vaccine efficacy of aQIV versus non-influenza comparator (Boostrix[®]) when administered as a single dose to prevent first occurrence RT-PCR-confirmed influenza, due to any strain of influenza regardless of antigenic match to the strains selected for the seasonal vaccine, in subjects \geq 65 years of age.

Primary Safety Objectives:

2. To evaluate the safety of aQIV through assessment for local and systemic solicited adverse events through Day 7 in a subset of subjects.
3. To evaluate the rates in each vaccine group of medically-attended adverse events within 30 days after the first occurrence RT-PCR confirmed ILI.
4. To evaluate the rates in each vaccine group of unsolicited adverse events for 21 days after vaccination and adverse events leading to withdrawal, serious adverse events (SAEs), adverse events of special interest (AESI), and new onset of chronic diseases (NOCD) for 365 days after vaccination.

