2.2 Secondary Objective(s)

Key Secondary Efficacy Objective:

1. To demonstrate absolute vaccine efficacy of aQIV versus non-influenza comparator when administered as a single dose to prevent first occurrence culture-confirmed influenza, due to strains antigenically matched to the strains selected for the seasonal vaccine.

Secondary Efficacy Objectives:

2. To evaluate absolute vaccine efficacy of aQIV versus non-influenza comparator when administered as a single dose to prevent first occurrence culture-confirmed influenza, due to any strain of influenza regardless of antigenic match to the strains selected for the seasonal vaccine.

3. To evaluate absolute vaccine efficacy of aQIV versus non-influenza comparator when administered as a single dose to prevent first occurrence culture-confirmed influenza, due to strains antigenically unmatched to the strains selected for the seasonal influenza vaccine.
4. To evaluate the absolute efficacy of aQIV versus non-influenza comparator when administered as a single dose to prevent first occurrence RT-PCR-confirmed influenza due to any strain of influenza regardless of antigenic match from 7 days to 180 days after vaccination or at the end of influenza season, whichever is longer (early efficacy).

Secondary Immunogenicity Objective:

5. To evaluate the immunogenicity of aQIV measured by HI titer 21 days after vaccination, against influenza strains homologous to the seasonal vaccine.

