3.5 Collection of Clinical Specimens

The following clinical specimens are required to be collected from each subject in this study:

- Nasopharyngeal swabs (as needed from subjects experiencing symptoms that meet primary protocol-defined ILI criteria).

The following clinical specimens are required to be collected from subjects participating in the immunogenicity subset:

- Blood at the Day 1 and 22 clinic visit

Collection and processing of each specimen should be completed by a qualified site member and in accordance with the study-specific Laboratory Manual. Testing of clinical specimens will be performed by a Seqirus or designated laboratory. Refer to the study-specific Laboratory Manual for additional details.

Blood Specimens

Approximately 10 mL sample of blood will be drawn from approximately 2800 subjects participating in the immunogenicity season at Days 1 and 22. The blood volume will not exceed 10 mL at each time point in order to provide the necessary serum volume (approximately half of the blood draw volume) for the serology assays (see [Section 7, Assessments](#) for additional details).

The total amount of blood collected over the study period per subject will be approximately 20 mL.

Nasopharyngeal Swabs

Subjects, who from Visit 1 (Day 1) onwards, experience symptoms meeting the primary protocol-defined ILI criteria (i.e. at least one of the following respiratory symptoms (new onset or exacerbation of pre-existing condition): sore throat, cough, sputum production,

wheezing, or difficulty breathing concurrently with at least one of the following systemic symptoms: temperature of $> 37.2^{\circ}\text{C} / 99^{\circ}\text{F}$, chills, tiredness, headache, or myalgia), will have one NP swab collected for evaluation of the presence of influenza virus by RT-PCR. The NP swab will be collected as soon as possible within 3 days of ILI onset, but collection up to 6 days will be permitted.

All samples will also be cultured for the growth of the strain of influenza obtained from the subjects in order to conduct antigenic characterization (to determine whether the clinical isolate is antigenically matched or antigenically unmatched to the vaccine strain).

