7.2 Efficacy Assessment

Confirmation of influenza infection by RT-PCR or culture from a nasopharyngeal swab sample is necessary for the efficacy assessment in the study. Nasopharyngeal swab retrieval will be initiated after primary protocol-defined ILI has been identified. Primary protocol-defined ILI can occur at any time during the study and will be evaluated in each subject from Visit 1 (Day 1) through Study Termination. ILI symptoms will be captured during study visits. The ILI onset day is defined as the first day that the subject meets the primary protocol-defined ILI. The end date is defined as the date the last symptom resolves. A new ILI episode will only be taken into account after resolution of the previous one, as judged by the investigator (suggested interval between two ILI episodes is 14 symptom-free days).

Subjects with primary protocol defined ILI will have a NP swab collected for evaluation of the presence of influenza virus. NP swabs should be targeted for collection within 3 days from the ILI onset to ensure optimal viral yield, however samples will be accepted if collected up to 6 days following the day of ILI onset. NP swabs will not be taken beyond a total of 7 days (6 days following onset of ILI) as the level of virus detectable beyond this period can be negligible, particularly for influenza A.

All NP swabs collected from subjects with ILI will be shipped under pre-specified conditions in viral transport media to a qualified lab and stored for analysis for influenza.

NP swabs will be analyzed by RT-PCR and placed into culture. The result of the RT-PCR assay will be the presence or absence of influenza virus. The viral culture will be used for the purpose of viral expansion to enable phenotypic characterization of the influenza virus (e.g. antigenic match). Testing will be conducted by a designated laboratory in a blinded manner towards the treatment arm. Please see the Protocol Ancillary Document for name(s) and details.

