8.4.4.3 Analysis of Exploratory Immunogenicity Objective(s)

Exploratory objectives related to the MN-assay will be evaluated using methods for lognormal and binomial data as described in the [Section 8.4.3.3.3](#).

Evaluation of a Serological Predictor of Protection Against Influenza

The immunogenicity data of the blood draw 21 days after vaccination from all subjects reporting an influenza case and subjects randomized from the population without an influenza case serving as the control group will be used to evaluate the relationship between antibody levels tested with the HI assay and clinical protection from influenza.

The Prentice criterion will be used to assess, whether an immunologic correlate of protection can be determined.

To accommodate the criterion a linear logistic regression model will be fitted with vaccine group included as independent predictor and incidence of influenza as dependent variable to show that the observed vaccine effect be explained in a statistical model using immunologic data.

A second logistic regression model will be fitted, adjusted for log-transformed antibody titer and vaccine group to determine the effect of antibody titer on the incidence of influenza. Then, the relationship between the occurrence of influenza and antibody titer level will be modeled using the logistic regression model advocated by Dunning that accommodates both antibody titers and factors independent of antibody titers.

In this model, the probability that a subject develops influenza is the probability that the subject is susceptible multiplied by the probability that susceptible individuals develop disease. Susceptibility is characterized by the probability l , and the probability that a subject with titer t is protected is represented by a 2-parameter logit function. Analyses will be conducted to determine the level of HI (or other assays that might be performed) antibody titer associated with 50%, 60%, 70%, 80% and 90% probability of protection.

The statistical and modelling considerations of estimating correlates of protection will further described in the SAP.

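### The correlate-of-protection analysis has no rule that influenza onset must follow the Day 22 blood draw, so cases ill before the draw can enter with a titre measured after the outcome

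*SAP*

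**What the plan says.** SAP section 11.4 and Protocol section 8.4.4.3 describe the analysis in the same words. The predictor comes from "The immunogenicity data of the blood draw 21 days after vaccination from all subjects reporting an influenza case", and the control group is a random selection of subjects without a case. Three models follow: two logistic regressions supporting a Prentice assessment, and a scaled-logit model giving the titres for 50% to 90% protection.

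The other passages that bear on the timing of cases are these:

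- The protocol's Definitions list has "Influenza case: An ILI associated with RT-PCR or culture confirmed influenza", with no day limit.
- Protocol section 3.5 provides for swabs from "Subjects, who from Visit 1 (Day 1) onwards, experience symptoms meeting the primary protocol-defined ILI criteria".
- Protocol section 7.2 says that ILI "will be evaluated in each subject from Visit 1 (Day 1) through Study Termination".
- Protocol section 2.1 ties the primary and secondary efficacy objectives to "cases of influenza occurring from 21 through 180 days after vaccination" (or season end, if later). It says nothing about the exploratory objectives.
- Protocol section 2.2 has a secondary objective counting cases "from 7 days to 180 days after vaccination or at the end of influenza season", so confirmed cases before Day 22 are foreseen.
- Protocol section 8.4.4.3 closes with "The statistical and modelling considerations of estimating correlates of protection will further described in the SAP". SAP section 11.4 adds no onset rule.
- The Day 22 visit window is -1 to +4 days (Protocol Table 2), so the draw falls between Day 21 and Day 26.
- SAP section 4.1 limits blood sampling to 2,800 subjects in one season, 1,400 per arm.

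**The concern.** A predictor of protection has to be measured before the outcome that it predicts. For a subject whose influenza precedes the draw it is not, and this matters in two ways.

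1. Infection itself may raise the Day 22 titre. A comparator subject infected early then looks like someone who had a high titre and was not protected.
2. Protocol section 7.3 says that antibody typically peaks after three weeks. An aQIV subject infected in the first days is credited with a vaccine titre that was not yet there at exposure. This needs no infection-induced rise.

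Both put cases at high titres and flatten the fitted slope. The slope determines how far the 80% and 90% protection titres lie above the 50% titre, and it also enters the titre-adjusted model used for the Prentice assessment. The problem is separate from how controls are sampled or weighted.

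**Working it through.** **The plan's own figure.** The documents give no case count for the correlate analysis, so I checked the attack rates that feed it. SAP section 5 assumes 3.5% (comparator) and 1.4% (aQIV) with 4,860 evaluable subjects per group: 4,860 x (0.035 + 0.014) = 238.1, which reproduces the planned 238 events.

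**Cases with a Day 22 sample.** 1,400 x (0.035 + 0.014) = 68.6, or 61.7 after 10% drop-out.

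**Early cases.** The efficacy window, days 21 through 180, spans at least 160 days; days 0 to 20 span 21. If the hazard in days 0 to 20 is m times the later hazard, early cases = 68.6 x (21/160) x m. The documents do not give m; I took 0.1 to 1.0.

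| m | Early cases | Share of all cases |
|---|---|---|
| 0.1 | 0.9 | 1.3% |
| 0.25 | 2.3 | 3.2% |
| 0.5 | 4.5 | 6.2% |
| 1.0 | 9.0 | 11.6% |

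A season running past day 180 would lower these numbers.

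**Effect of infection-raised titres.** I fitted the scaled-logit model by expected likelihood, with and without early cases. Assumed inputs: SD 1.6 on the log2 scale; comparator geometric mean titre 15; 64% of aQIV subjects at or above 1:40; true slope 1.0 or 1.5 per log2; early cases starting from comparator-type titres, multiplied by the stated rise.

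| Early cases, rise | Slope 1.0: fitted slope; 50% / 90% titre | Slope 1.5: fitted slope; 50% / 90% titre |
|---|---|---|
| none | 1.00; 15 / 69 | 1.50; 24 / 66 |
| 2, 4-fold | 0.95; 15 / 75 | 1.39; 24 / 72 |
| 5, no rise | 1.01; 15 / 66 | 1.50; 23 / 64 |
| 5, 8-fold | 0.71; 11 / 92 | 0.94; 20 / 102 |
| 9, 4-fold | 0.84; 17 / 102 | 1.16; 27 / 99 |
| 9, 8-fold | 0.57; 8 / 111 | 0.73; 18 / 143 |

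The slope flattens whenever titres are raised. The 90% titre usually rises, but not always: with 9 early cases, a 16-fold rise and true slope 1.0, the fit degenerates (slope 0.34, 90% titre 6).

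**Effect of a vaccine response not yet present.** In a second set of assumptions, log2 titres are N(4, 1.6) for comparator and N(6.5, 1.6) for aQIV at Day 22, and risk is 0.05 x (1 - expit(-6 + 1.2 x log2 titre)). This gives about 65 later cases and true 50% / 90% titres of 32 / 114. Early cases are split equally between arms, with risk driven by the baseline titre and a constant aQIV rise of 2.5 log2.

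| Early cases | 90% titre, no infection rise | 90% titre, 8-fold rise in 60% of early comparator cases |
|---|---|---|
| 1 | 117 | 121 |
| 2 | 121 | 129 |
| 5 | 131 | 153 |
| 9 | 146 | 192 |

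In all of these runs the 50% titre stays between about 32 and 33.

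**Would the efficacy window be enough?** With a draw as late as Day 26, onsets up to four days into that window can still precede it. At a uniform hazard that is at most 68.6 x 4/160 = 1.7 cases, reached only if every draw is taken on the last permitted day.

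**The case against.** The strongest reply is that the text is silent on onset rather than wrong. Neither document says that the correlate uses cases from Day 1, and the SAP counts cases from 21 days in its primary endpoint (section 2.1.2) and interim rules (section 14.1). A programmer could carry that window over. This stands in part: intent cannot be read from the documents. But the SAP writes the window out where it wants it, section 11.4 does not, and the general definition has no limit. Carrying the window over would also leave the late-draw gap and would not keep early cases out of the controls.

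A reader might infer several stronger things that the documents do not support.

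- *Every trial case enters.* Only subjects with a Day 22 sample can, from about 2,800 bled in one season.
- *All the 50% to 90% titres shift.* In most runs the fitted and true curves cross, so some intermediate titre does not move.
- *The 90% titre is overstated by a fixed large percentage.* That would need a known number of early cases and a known infection rise, and neither is given. An early share above about 12% would need a higher hazard just after vaccination than later, for which nothing in the plan argues. Exclusion criterion 15 (acute respiratory symptoms at screening) points the other way.

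Precision is also low. Under the second set of assumptions the asymptotic 95% interval for the 90% titre is about 63 to 205 around 114, and even the largest value in that table (192) lies inside it. That limits what the analysis can show but does not excuse an avoidable bias. Finally, the objective is exploratory, testing of the sera is optional, and no success criterion depends on it. All of that stands and limits the weight of the point.

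**Conclusion.** The point holds. As written, the rule admits cases whose Day 22 titre was measured after the illness. The direction is reasonably clear: a flatter titre-risk slope and, in most runs, overstated upper (80% to 90%) protection titres, with the 50% titre moving either way or hardly at all.

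The size is not known. With one early case the 90% titre rises by about 3% to 6% (114 to 117 or 121). With two and a 4-fold rise it goes up by about 9% (69 to 75, or 66 to 72). With five and an 8-fold rise it goes up by about a third to a half (69 to 92, 66 to 102). With nine it can more than double (66 to 143). These figures rest on assumed titre distributions, slopes, infection rises and early hazards; the documents supply only the attack rates, the number bled and the windows. If early cases had neither an infection rise nor a vaccine response by the draw, the titres would hardly move.

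The primary, key secondary, safety and CBER immunogenicity conclusions do not depend on this analysis. The change is worth making because it is nearly free and is credible only if set before titres and cases are seen together.

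**What to change.** In SAP section 11.4 and Protocol section 8.4.4.3:

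- Restrict the correlate models, cases and controls alike, to subjects with no confirmed influenza on or before their own Day 22 draw.
- Count as a case the first RT-PCR-confirmed influenza with ILI onset after that draw and through the end of the primary efficacy window.
- Report the number of subjects excluded, by arm.

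A sensitivity analysis with a short lag after the draw would be a useful addition. The cost is a sentence or two in each document and no new data. A few cases are lost from an exploratory analysis: about 1 to 9 under the assumptions above, plus at most about 2 from late draws.
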